6.3.1 Outcome variables

Primary Effectiveness outcomes of interest: (definitions provided in **Appendix A**):

- **Primary Outcome:** VTE

Safety outcomes of interest:

1. Major bleeding

6.3.2 Study follow-up

Both as-treated (AT) and intention-to-treat (ITT) analyses will be conducted with treatment defined as the index drug on the day of cohort entry. Because adherence in the real-world databases is expected to be much worse than in the trial, the AT analysis is the **primary** analysis, as it targets the relative hazard of outcomes on treatment.

For the AT analyses, the follow-up will start the day after initiation of rivaroxaban and comparator and will continue until the earliest date of the following events:

- The first occurrence of the outcome of interest, unless otherwise specified for selected outcomes,
- The date of end of continuous registration in the database,
- End of the study period,
- Measured death event occurs,
- Nursing home admission
 - Nursing home admissions are considered a censoring event because the data sources utilized typically provide little to no data on a patient, particularly on drug utilization, after admission. We will utilize this as an exclusion reason for cohorts for the same reason.
- The date of drug discontinuation, defined as the date of the last continuous treatment episode of the index drug (rivaroxaban and comparator) plus a defined grace period (i.e., 10 days after the end of the last prescription's days' supply in main analyses).
- The date of augmentation or switching from exposure to comparator or vice versa or augmentation/switching to any other NOAC (e.g. switching from rivaroxaban to apixaban would be a censoring event);
 - A dosage change on the index treatment does not fulfill this criterion
 - An added treatment that is not part of the exposure or comparator group does not fulfill this criterion

For the intention-to-treat (ITT) analyses, the censoring based on the augmentation/switching and treatment discontinuation will be replaced with a maximum allowed follow-up time of 365 days.

7. Initial Feasibility Analysis

Action report name:

Optum- <https://bwh-dope.aetion.com/projects/details/1527/rwrs/66276>

MarketScan- <https://bwh-dope.aetion.com/projects/details/1653/rwrs/66277>

Medicare- <https://bwh-dope.aetion.com/projects/details/1525/rwrs/67892>

Date conducted: 02/24/2021

Complete Aetion feasibility analysis using age, sex, and CCI as the only covariates and the primary endpoint (Section 6.3.1) as the outcome. No measures of association will be computed nor will incidence rates stratified by treatment group.

- Report patient characteristics by treatment group

Variable	Optum			Truven			Medicare		
	Reference-warfarin	Exposure - rivaroxaban	Difference	Reference-warfarin	Exposure - rivaroxaban	Difference	Reference-warfarin	Exposure - rivaroxaban	Difference
Number of patients	10,916	6,439	- (-, -)	22,999	9,389	- (-, -)	32,895	16,223	- (-, -)
Age									
...mean (sd)	62.06 (15.66)	60.27 (15.41)	1.79 (1.31, 2.27)	55.59 (15.02)	53.62 (14.45)	1.98 (1.63, 2.33)	75.46 (7.25)	74.46 (6.75)	1.00 (0.87, 1.13)
...median [IQR]	65.00 [51.00, 74.00]	62.00 [50.00, 72.00]	- (-, -)	56.00 [46.00, 64.00]	54.00 [44.00, 63.00]	- (-, -)	74.00 [69.00, 80.00]	73.00 [69.00, 79.00]	- (-, -)
Gender without unknown									
...Male; n (%)	4,950 (45.3%)	3,030 (47.1%)	-1.7% (-3.3%, -0.2%)	11,058 (48.1%)	4,685 (49.9%)	-1.8% (-3.0%, -0.6%)	12,293 (37.4%)	6,712 (41.4%)	-4.0% (-4.9%, -3.1%)
...Female; n (%)	5,965 (54.6%)	3,408 (52.9%)	1.7% (0.2%, 3.3%)	11,941 (51.9%)	4,704 (50.1%)	1.8% (0.6%, 3.0%)	20,602 (62.6%)	9,511 (58.6%)	4.0% (3.1%, 4.9%)
CCI (180 days)- ICD9 and ICD10 v2									
...mean (sd)	3.04 (2.20)	3.21 (2.00)	-0.18 (-0.24, -0.11)	2.11 (1.91)	2.43 (1.82)	-0.32 (-0.36, -0.28)	6.33 (3.30)	6.24 (3.08)	0.09 (0.03, 0.15)
...median [IQR]	3.00 [1.00, 4.00]	3.00 [2.00, 4.00]	- (-, -)	2.00 [1.00, 3.00]	2.00 [1.00, 3.00]	- (-, -)	6.00 [4.00, 8.00]	6.00 [4.00, 8.00]	- (-, -)

- Report summary parameters of study population **FEASIBILITY- FOR STUDY OUTCOME**

FEASIBILITY- FOR STUDY OUTCOME			
Variable	Optum	Truven	Medicare
Value	Value	Value	Value
Number of patients in full cohort	17,384	32,445	49,118
Number of patients dropped as incomplete cases	0	0	0
Number of patients that did not begin follow-up	29	57	77
Number of patients in analytic cohort	17,355	32,388	49,041
Number of events	232	482	669
Number of person-years	6,152.63	12,258.57	20,258.62
Number of patients in group: Reference- warfarin	10,916	22,999	32,848
Number of patients in group: Exposure - rivaroxaban	6,439	9,389	16,193
Risk per 1,000 patients	13.37	14.88	13.64
Rate per 1,000 person-years	37.71	39.32	33.02

- Report median follow-up time by treatment group

MEDIAN FOLLOW-UP TIME FOR STUDY OUTCOME			
Median Follow-Up Time (Days) [IQR]			
	Optum	Truven	Medicare

Patient Group	Median Follow-Up Time (Days) [IQR]	Median Follow-Up Time (Days) [IQR]	Median Follow-Up Time (Days) [IQR]
Overall Patient Population	76 [38, 174]	93 [38, 183]	98 [38, 196]
Referent	82 [38, 177]	96 [43, 184]	103 [43, 201]
Exposure	65 [38, 171]	84 [38, 180]	82 [38, 185]

- Report reasons for censoring in the overall study population

CENSORING REASONS FOR STUDY OUTCOME			
	Optum	Truven	Medicare
Outcome	232 (1.3%)	482 (1.5%)	669 (1.4%)
Death	118 (0.7%)	63 (0.2%)	1,199 (2.4%)
Start of an additional exposure	606 (3.5%)	1,277 (3.9%)	2,077 (4.2%)
End of index exposure	12,371 (71.3%)	25,197 (77.8%)	37,423 (76.3%)
Specified date reached	476 (2.7%)	709 (2.2%)	3,194 (6.5%)
End of patient data	0 (0.0%)	0 (0.0%)	0 (0.0%)
End of patient enrollment	1,340 (7.7%)	4,035 (12.5%)	833 (1.7%)
Censoring - Switch to other NOAC + nursing home Occurred	2,212 (12.7%)	625 (1.9%)	3,646 (7.4%)

- Report overall risk of the primary outcome.

	Optum	Marketscan	Medicare	Pooled
Risk per 1,000 patients	13.37	14.88	13.64	13.98

8. Initial Power Assessment

Action report name:

For rivaroxaban vs. warfarin

Optum- <https://bwh-dope.aetion.com/projects/details/1527/rwrs/66281>

MarketScan- <https://bwh-dope.aetion.com/projects/details/1653/rwrs/66280>

Mediare- <https://bwh-dope.aetion.com/projects/details/1525/rwrs/67893>

Date conducted: 02/24/2021

In order to complete the initial power analysis, the dummy outcome of a 90-day gap in database enrollment will be used. This outcome is used to ensure that no information on the comparative risks of the outcomes of interest are available at this stage. Complete a 1:1 PS-matched comparative analysis using this outcome. PS should include only 2 covariates: age and combined comorbidity index. Power calculations are based on the formulas from Chow et al. (2008).

- Stop analyses until feasibility and power are reviewed by primary investigators and FDA. Reviewers evaluate the results of the analyses described above in Sections 7 and 8, including numbers of patients, patient characteristics, follow-up time, and reasons for censoring by treatment group, as well as overall rates of outcomes and study power. These parameters are re-evaluated and reported in the subsequent sections, after incorporating feedback and refining the protocol.

- Pooled

Non-inferiority Analysis	
Number of patients matched	64,038
Reference	32,019
Exposed	32,019
Risk per 1,000 patients	13.98
Assumed HR from RCT	1.12
Alpha (2-sided)	0.05
Non-inferiority margin	2
Number of events expected	895.25124
Power	1

- Optum

Non-inferiority Analysis	
Number of patients matched	12,876
Reference	6,438
Exposed	6,438
Risk per 1,000 patients	13.37
Assumed HR from RCT	1.12
Alpha (2-sided)	0.05
Non-inferiority margin	2
Number of events expected	172.15212
Power	0.967396851

- MarketScan

Non-inferiority Analysis	
Number of patients matched	18,776
Reference	9,388
Exposed	9,388
Risk per 1,000 patients	14.88
Assumed HR from RCT	1.12
Alpha (2-sided)	0.05
Non-inferiority margin	2
Number of events expected	279.38688
Power	0.998048094

○ Medicare

Non-inferiority Analysis	
Number of patients matched	32,386
Reference	16,193
Exposed	16,193
Risk per 1,000 patients	13.64
Assumed HR from RCT	1.12
Alpha (2-sided)	0.05
Non-inferiority margin	2
Number of events expected	441.74504
Power	0.999982118

- Stop analyses until balance and final power assessment are reviewed by primary investigators, FDA, and assigned members of advisory board.

Reviewed by PI:		Date reviewed:	
Reviewed by FDA:		Date reviewed:	
Reasons for stopping analysis (if required):			

9. Balance Assessment

Action report links:

Optum: <https://bwh-dope.aetion.com/projects/details/1527/rwrs/67705>

Marketscan: <https://bwh-dope.aetion.com/projects/details/1653/rwrs/67706>

Medicare: <https://bwh-dope.aetion.com/projects/details/1525/rwrs/67894>

Date conducted: 3/28/2021

After review of initial feasibility and power analyses, complete creation of the remaining covariates from Section 6.2. Again, using the dummy outcome of a 90-day gap in database enrollment, complete a 1:1 PS-matched analysis. The PS should include the complete list of covariates.

- Provide plot of PS distributions stratified by treatment group.

Note- Please refer to **Appendix B**.

- Report covariate balance after matching.

Note- Please refer to **Appendix B**.

- Report reasons for censoring by treatment group.

	Overall	Referent	Exposure
Dummy outcome	0 (0.0%)	0 (0.0%)	0 (0.0%)
Death	477 (1.50%)	218 (1.37%)	259 (1.63%)
Start of an additional exposure	1,584 (4.98%)	1,023 (6.44 %)	561 (3.53%)
End of index exposure	23,632 (74.35%)	11,350 (71.42%)	12,282 (77.28%)
Specified date reached	1,617 (5.09%)	875 (5.51%)	742 (4.67%)
End of patient enrollment	2,079 (6.54%)	1,046 (6.58%)	1,033 (6.50%)
Switch to other NOACs (for censoring) + nursing home admission	2,397 (7.54%)	1,381 (8.69%)	1,016 (6.39%)

- Report follow-up time by treatment group.

Median Follow-Up Time (Days) [IQR]			
Patient Group	Optum	MarketScan	Medicare
Overall Patient Population	70 [36-174]	91 [38-184]	97 [38-195]
Referent	75 [38-173]	92 [40-178]	100 [41-199]
Exposure	65 [33-175]	91 [38-188]	88 [38-190]

10. Final Power Assessment

Date conducted: 03/28/2021

- Re-calculate power in the appropriate excel table, using the revised number of matched patients from the PS-match in Section 9. All other parameters in the table should be the same as in Section 8.

Pooled

Non-inferiority Analysis	
Number of patients matched	32,998
Reference	16,499
Exposed	16,499
Risk per 1,000 patients	13.87
Assumed HR from RCT	1.12
Alpha (2-sided)	0.05
Non-inferiority margin	2
Number of events expected	457.68226
Power	0.999988934

Optum

Non-inferiority Analysis	
Number of patients matched	4,306
Reference	2,153
Exposed	2,153
Risk per 1,000 patients	13.37
Assumed HR from RCT	1.12
Alpha (2-sided)	0.05
Non-inferiority margin	2
Number of events expected	57.57122
Power	0.594735156

Marketscan

Non-inferiority Analysis	
Number of patients matched	11,350
Reference	5,675
Exposed	5,675
Risk per 1,000 patients	14.88
Assumed HR from RCT	1.12
Alpha (2-sided)	0.05
Non-inferiority margin	2
Number of events expected	168.888
Power	0.964666171

Medicare

Non-inferiority Analysis	
Number of patients matched	17,342
Reference	8,671
Exposed	8,671
Risk per 1,000 patients	13.46
Assumed HR from RCT	1.12
Alpha (2-sided)	0.05
Non-inferiority margin	2
Number of events expected	233.42332
Power	0.993231623

- Stop analyses until balance and final power assessment are reviewed by primary investigators, FDA, and assigned members of advisory board.

Reviewed by PI:		Date reviewed:	
Reviewed by FDA:		Date reviewed:	
Reasons for stopping analysis (if required):			

11. Study Confidence and Concerns

Deadline for voting on study confidence and listing concerns:

Date votes and concerns are summarized:

- If final feasibility and power analyses are reviewed and approved, proceed to the remaining protocol steps.
- All study team and advisory board members that review this protocol should at this stage provide their level of confidence for the success of the RWD study in the [Google Form](#). This form also provides space for reviewers to list any concerns that they feel may contribute to a failure to replicate the findings of the RCT, including differences in study populations, poor measurement of study variables, or residual confounding. All responses will be kept confidential and individual-level results will only be shared with the individual respondent.
- After the deadline for voting has passed, provide the distribution of responses and summarize all concerns here.

12. Register study protocol on clinicalTrials.gov

Date conducted:

- Register the study on [clinicalTrials.gov](#) and upload this document.

13. Comparative Analyses

Action report name:

Date conducted:

13.1 For primary analysis:

13.2 For sensitivity analyses:

14. Requested Results

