1.3 Primary endpoint for replication

The primary outcome of the study was symptomatic, recurrent VTE

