5.1 Cohort Summary

This study will involve a new user, parallel group, propensity score-matched, retrospective cohort study design comparing rivaroxaban to warfarin users. The patients will be required to have continuous enrollment during a baseline period of 180 days before initiation of rivaroxaban or warfarin (index date). We will restrict the analyses to patients with a diagnosis of PE.

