Appendix A

Title

Venous Thromboembolism (VTE)

ICD-9 Dx inpatient primary position

PE

- 415.1 PULMONARY EMBOLISM AND INFARCTION
- 415.11 IATROGENIC PULMONARY EMBOLISM AND INFARCTION
- 415.19 OTHER PULMONARY EMBOLISM AND INFARCTION

DVT

- 451.1 PHLEBITIS AND THROMBOPHLEBITIS OF DEEP VEINS OF LOWER EXTREMITIES
- 451.11 PHLEBITIS AND THROMBOPHLEBITIS OF FEMORAL VEIN (DEEP) (SUPERFICIAL)
- 451.19 PHLEBITIS AND THROMBOPHLEBITIS OF OTHER
- 451.2 PHLEBITIS AND THROMBOPHLEBITIS OF LOWER EXTREMITIES UNSPECIFIED
- 451.81 PHLEBITIS AND THROMBOPHLEBITIS OF ILIAC VEIN
- 451.9 PHLEBITIS AND THROMBOPHLEBITIS OF UNSPECIFIED SITE
- 453 BUDD-CHIARI SYNDROME
- 453.1 THROMBOPHLEBITIS MIGRANS
- 453.2 EMBOLISM AND THROMBOSIS OF INFERIOR VENA CAVA
- 453.4 ACUTE VENOUS EMBOLISM AND THROMBOSIS OF DEEP VESSELS OF LOWER EXTREMITY
- 453.4 ACUTE VENOUS EMBOLISM AND THROMBOSIS OF UNSPECIFIED DEEP VESSELS OF LOWER EXTREMITY
- 453.41 ACUTE VENOUS EMBOLISM AND THROMBOSIS OF DEEP VESSELS OF PROXIMAL LOWER EXTREMITY
- 453.42 ACUTE VENOUS EMBOLISM AND THROMBOSIS OF DEEP VESSELS OF DISTAL LOWER EXTREMITY
- 453.5 CHRONIC VENOUS EMBOLISM AND THROMBOSIS OF DEEP VESSELS OF LOWER EXTREMITY
- 453.5 CHRONIC VENOUS EMBOLISM AND THROMBOSIS OF UNSPECIFIED DEEP VESSELS OF LOWER EXTREMITY
- 453.51 CHRONIC VENOUS EMBOLISM AND THROMBOSIS OF DEEP VESSELS OF PROXIMAL LOWER EXTREMITY
- 453.52 CHRONIC VENOUS EMBOLISM AND THROMBOSIS OF DEEP VESSELS OF DISTAL LOWER EXTREMITY
- 453.8 ACUTE VENOUS EMBOLISM AND THROMBOSIS OF OTHER SPECIFIED VEINS
- 453.82 ACUTE VENOUS EMBOLISM AND THROMBOSIS OF DEEP VEINS OF UPPER EXTREMITY
- 453.83 ACUTE VENOUS EMBOLISM AND THROMBOSIS OF UPPER EXTREMITY UNSPECIFIED
- 453.84 ACUTE VENOUS EMBOLISM AND THROMBOSIS OF AXILLARY VEINS
- 453.85 ACUTE VENOUS EMBOLISM AND THROMBOSIS OF SUBCLAVIAN VEINS
- 453.86 ACUTE VENOUS EMBOLISM AND THROMBOSIS OF INTERNAL JUGULAR VEINS
- 453.87 ACUTE VENOUS EMBOLISM AND THROMBOSIS OF OTHER THORACIC VEINS
- 453.89 ACUTE VENOUS EMBOLISM AND THROMBOSIS OF OTHER SPECIFIED VEINS

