Appendix A

453.9

EMBOLISM AND THROMBOSIS OF UNSPECIFIED SITE

ICD-10 Dx inpatient primary position

PE

- I26.0 Pulmonary embolism with acute cor pulmonale
- I26.01 Septic pulmonary embolism with acute cor pulmonale
- I26.02 Saddle embolus of pulmonary artery with acute cor pulmonale
- I26.09 Other pulmonary embolism with acute cor pulmonale
- I26.9 Pulmonary embolism without acute cor pulmonale
- I26.99 Other pulmonary embolism without acute cor pulmonale

DVT

- I80.1 Phlebitis and thrombophlebitis of femoral vein
- I80.10 Phlebitis and thrombophlebitis of unspecified femoral vein
- I80.11 Phlebitis and thrombophlebitis of right femoral vein
- I80.12 Phlebitis and thrombophlebitis of left femoral vein
- I80.13 Phlebitis and thrombophlebitis of femoral vein, bilateral
- I80.2 Phlebitis and thrombophlebitis of other and unspecified deep vessels of lower extremities
- I80.20 Phlebitis and thrombophlebitis of unspecified deep vessels of lower extremities
- I80.201 Phlebitis and thrombophlebitis of unspecified deep vessels of right lower extremity
- I80.202 Phlebitis and thrombophlebitis of unspecified deep vessels of left lower extremity
- I80.203 Phlebitis and thrombophlebitis of unspecified deep vessels of lower extremities, bilateral
- I80.209 Phlebitis and thrombophlebitis of unspecified deep vessels of unspecified lower extremity
- I80.21 Phlebitis and thrombophlebitis of iliac vein
- I80.211 Phlebitis and thrombophlebitis of right iliac vein
- I80.212 Phlebitis and thrombophlebitis of left iliac vein
- I80.213 Phlebitis and thrombophlebitis of iliac vein, bilateral
- I80.219 Phlebitis and thrombophlebitis of unspecified iliac vein
- I80.22 Phlebitis and thrombophlebitis of popliteal vein
- I80.221 Phlebitis and thrombophlebitis of right popliteal vein
- I80.222 Phlebitis and thrombophlebitis of left popliteal vein
- I80.223 Phlebitis and thrombophlebitis of popliteal vein, bilateral
- I80.229 Phlebitis and thrombophlebitis of unspecified popliteal vein
- I80.23 Phlebitis and thrombophlebitis of tibial vein
- I80.231 Phlebitis and thrombophlebitis of right tibial vein

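### The outcome rule for recurrent VTE has no visible provision to separate a new event from a transfer or admission for the index PE

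*Combined protocol and SAP*

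**What the plan says.** Section 1.3 sets the target: "The primary outcome of the study was symptomatic, recurrent VTE". Section 5.1 fixes the population: "We will restrict the analyses to patients with a diagnosis of PE". The same section takes drug initiation as the index date, not the PE admission or discharge.

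Section 6.3.1 lists the primary outcome only as VTE and leaves the definition to Appendix A. There the PE and DVT codes stand under "ICD-9 Dx inpatient primary position" and "ICD-10 Dx inpatient primary position", with no further condition. The list also holds chronic DVT codes (453.5x and I82.5x), for example "CHRONIC VENOUS EMBOLISM AND THROMBOSIS OF DEEP VESSELS OF LOWER EXTREMITY".

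In the as-treated analysis of Section 6.3.2, "the follow-up will start the day after initiation of rivaroxaban and comparator", and it ends at "The first occurrence of the outcome of interest, unless otherwise specified for selected outcomes" if no other censoring reason comes earlier. No exception is specified for VTE. The intention-to-treat text changes only the censoring, so it inherits the same start and event rule. Nowhere in the visible text is it said whether an event is dated by admission, claim or discharge.

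**The concern.** Everyone in the cohort has a PE at entry, and the PE and DVT outcome codes also describe that condition. A claims rule for recurrence therefore needs something that marks an event as new: an admission date after the index stay, a gap, or linkage of transfers. None is visible. The primary-position requirement removes admissions in which PE is only a secondary code. It does not remove a transfer or admission for the index PE itself, which can also carry PE first.

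Events are rare (about 14 per 1,000 patients in Section 7), so a modest number of misclassified admissions could be a material share of the endpoint. Carry-over events reflect the index episode, not the study drug. If they occur about equally in both arms they dilute the HR, and in a non-inferiority comparison with a margin of 2.0 dilution is anti-conservative.

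**Working it through.** **1. Patients who start the drug without a recent admission.** This is the one route that the documents let us size. The inputs are the matched Appendix B row for any hospitalization within the prior 30 days and the matched total in the Section 9 censoring table (15,893 per arm). The Medicare denominator is obtained by subtraction: 15,893 − 2,153 − 5,675 = 8,065.

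| Database | N per arm | Warfarin, none | Rivaroxaban, none |
|---|---|---|---|
| Optum | 2,153 | 2,153 − 1,966 = 187 (8.7%) | 2,153 − 1,967 = 186 (8.6%) |
| MarketScan | 5,675 | 5,675 − 5,661 = 14 (0.2%) | 5,675 − 5,658 = 17 (0.3%) |
| Medicare | 8,065 | 8,065 − 7,617 = 448 (5.6%) | 8,065 − 7,655 = 410 (5.1%) |
| Pooled | 15,893 | 15,893 − 15,244 = 649 (4.1%) | 15,893 − 15,280 = 613 (3.9%) |

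Together this is 649 + 613 = 1,262 patients, or 1,262/31,786 = 4.0%. The number later admitted for the index PE is not reported. As an assumption, 1%, 2%, 5% or 10% of them would give about 13, 25, 63 or 126 events, which is 2.8%, 5.5%, 13.8% or 27.6% of 457.68. Transfers and readmissions among the other 96% would add to this and cannot be sized.

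**2. The plan's own power.** Section 10 gives 32,998 × 13.87/1,000 = 457.68 pooled events. With D events and 1:1 matching,

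power = Φ( √(D/4) × [ln 2 − ln HR] − 1.96 ).

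At HR 1.12 this is Φ(10.697 × 0.5798 − 1.96) = Φ(4.242) = 0.99999, matching the printed 0.999988934. The Optum figure (57.57 events, 0.5947) is also reproduced.

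**3. Equal carry-over.** Let f be the share of counted warfarin-arm events that are carry-over (not in the documents; assumed). With equal carry-over in both arms, observed HR ≈ f + (1 − f) × true HR. This treats the Cox HR as an event-weighted mix. The false non-inferiority probability at a true HR of 2.0 is Φ( 10.697 × ln(2/observed HR) − 1.96 ).

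| f | Observed HR, true 2.0 | False non-inferiority | Observed HR, true 1.12 |
|---|---|---|---|
| 0 | 2.00 | 2.5% | 1.12 |
| 5% | 1.95 | 4.6% | 1.114 |
| 10% | 1.90 | 7.9% | 1.108 |
| 20% | 1.80 | 20% | 1.096 |
| 30% | 1.70 | 41% | 1.084 |

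Section 10 uses more matched patients than the 31,786 in the Section 9 table. With 31,786 × 13.98/1,000 = 444 events, the four probabilities are 4.5%, 7.8%, 20% and 40%, so this discrepancy does not matter here.

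**4. Unequal carry-over.** Let k be the rivaroxaban-to-warfarin ratio of carry-over risk, so that observed HR ≈ f × k + (1 − f) × true HR. At f = 20% and a true HR of 1.12, the observed HR is 0.996 for k = 0.5, 1.096 for k = 1, 1.196 for k = 1.5 and 1.296 for k = 2. It lies between 1 and 1.12 only for k from about 0.52 to 1.12. At a true HR of 2.0 it is below 2.0 for any k below 2: false non-inferiority is 41%, 20%, 7.9% and 2.5% at k = 0.5, 1, 1.5 and 2, and falls to 0.65% at k = 2.5.

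**The case against.** **The direction is not shown.** A reader might infer that the rule necessarily pulls the HR toward 1. The documents do not establish this: no early events are reported by arm, and Section 7 bars rates by treatment group at that stage. Step 4 shows that a large imbalance could push the HR either way. This stands, and the direction is stated here only conditionally. Matching makes similar carry-over plausible: the no-admission counts are in the ratio 613/649 = 0.94, and mean hospital days are 5.84 and 5.77.

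**The unmatched table suggests more exposure than the analysis has.** Before matching, 7–11% of Optum and 5–13% of Medicare patients had no admission in the prior 30 days. The comparison is matched, so the smaller figures in step 1 apply.

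**The event data do not point to the no-admission route.** MarketScan, where this route is almost absent, has the highest event rate (39.32 per 1,000 person-years, against 37.71 in Optum and 33.02 in Medicare). This is a comparison across different populations and does not address transfers or readmissions, but it warns against assuming a large effect. A reader might also infer that the first admission of a patient without a recent stay would be the index PE. Nothing in the documents shows that.

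**Most index stays probably began before day 1.** About 96% of matched patients were hospitalized in the prior 30 days. If events are dated by admission, many index stays drop out on their own; the plan does not say that they are.

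**Part of the plan is not visible.** The design diagram is not shown, and the PE inclusion definition is not in the available text of Appendix A. A rule tied to the index stay could sit there. The outcome definition itself is visible and contains none.

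**Conclusion.** The gap is real: as written, a transfer or admission for the index PE can count as a recurrence. Its frequency is unknown, and so is the size of any bias. If carry-over is similar in both arms, the HR moves toward 1. The statement that non-inferiority is favoured is sturdier than that, because at a true HR of 2.0 it needs only a carry-over ratio below 2.

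The inflation figures in step 3 rest on an assumed carry-over share and on a true HR exactly at the margin. They show sensitivity and are not an estimate. At the plan's assumed HR of 1.12 the practical effect is small. The point deserves action because the remedy is cheap and Sections 13.1 and 13.2 are still empty, so no listed analysis would reveal the problem.

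**What to change.** - In Appendix A, define the outcome as a new admission whose admission date is after drug initiation and after discharge from any index PE stay. Link to the index stay any overlapping stay, any transfer, and any admission beginning within 1 day of discharge. For patients with no inpatient index PE, do not count an admission continuous with the index diagnosis. If such a rule already exists in the diagram or the inclusion definitions, repeat it here.
- In Section 13.2, pre-specify a sensitivity analysis that starts follow-up at day 15 in both arms.
- Report event counts by time since index, pooled over arms, before comparative results are seen. This respects the Section 7 restriction.

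**Cost.** One definition edit and one extra run. The delayed start loses some true early recurrences. With an assumed 30% fewer events, the power formula gives 0.999 pooled (320 events), 0.96 in Medicare and 0.88 in MarketScan. Optum falls from 0.59 to 0.45 (40 events), so the sensitivity analysis should be judged on the pooled result. A day-31 start is optional: the lower quartile of as-treated follow-up is about 33 to 43 days across the groups in Sections 7 and 9, so it would discard much of the on-treatment time.

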Appendix A

Trial Name (with web links)	EINSTEIN PE
Trial Name (with pdf links)	EINSTEIN PE
NCT	NCT00439777
Therapeutic Area	Cardiology/Vascular Diseases
Study batch	NOACs
Brand Name	Xarelto
Generic Name	Rivaroxaban
Sponsor	Bayer Johnson & Johnson Pharmaceutical Research & Development, L.L.C
Year	2012
Measurable endpoint	Percentage of Participants With Symptomatic Recurrent Venous Thromboembolism [VTE] (i.e. the Composite of Recurrent Deep Vein Thrombosis [DVT] or Fatal or Non-fatal Pulmonary Embolism [PE]) Until the Intended End of Study Treatment
Exposure	Rivaroxaban
Comparator	Enoxaparin/VKA
Population	Patients of legal age who had acute symptomatic pulmonary embolism with or without deep-vein thrombosis
Trial finding	HR = 1.12 (95% CI 0.75 to 1.68)
No. of Patients	4,832 (2,419 in exposed arm)
Non-inferiority margin	HR = 2.0
Assay Sens. Endpoint (from trial)	Percentage of Participants With the Composite Variable Comprising Recurrent DVT, Non-fatal PE and All Cause Mortality Until the Intended End of Study Treatment
Finding for potential Assay Sens. Outcome from trial-	HR = 0.85 (95% CI 0.63 to 1.14)
Power	0.90. Assuming equal efficacy, a total of 88 events was calculated to give a power of 90% to prove that rivaroxaban is at least as effective as the comparator, considering a non-inferiority upper CI margin for the hazard ratio of 2.0 (two-sided $\alpha=0.05$). A mean incidence for the primary efficacy outcome of 3% was expected and an enrollment of at least 3000 patients was necessary

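### The trial endpoint includes fatal PE, but the study counts only inpatient primary-diagnosis VTE codes and censors death, so a fatal PE without such a code is treated as event-free

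*Combined protocol and SAP*

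**What the plan says.** The trial table that opens Appendix A describes the endpoint to be emulated as a composite of recurrent DVT or "Fatal or Non-fatal Pulmonary Embolism [PE]) Until the Intended End of Study Treatment". Section 6.3.1 reduces this to "Primary Outcome: VTE" and refers to Appendix A for the definition. The code lists there are headed "ICD-9 Dx inpatient primary position" and "ICD-10 Dx inpatient primary position". No death record, cause of death, emergency-department code or outpatient code contributes.

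Section 6.3.2 lists "Measured death event occurs" among the events that end follow-up in the primary AT analysis. For ITT, "the censoring based on the augmentation/switching and treatment discontinuation will be replaced with a maximum allowed follow-up time of 365 days". The ITT rule does not touch the death criterion, so death censors there too.

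Appendix A also records, as the trial's assay-sensitivity endpoint, a composite of recurrent DVT, non-fatal PE and death from any cause, with HR 0.85 (95% CI 0.63 to 1.14). Sections 1.5 and 6.3.1 carry only major bleeding forward. Section 13.2, for sensitivity analyses, has a heading and no content. Table 3 (Section 14.3) asks for the number of deaths by treatment group.

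**The concern.** A patient whose recurrent PE is fatal at home, in transit or in the emergency department, or whose terminal admission is coded with another diagnosis first, contributes no primary event and leaves the risk set as if event-free. The part of the trial endpoint most at risk of being missed is the fatal part. The analysis also treats that exit as unrelated to VTE risk, which for a PE death it is not.

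What is at stake is the reach of the conclusion. A non-inferiority result on hospitalised VTE would be reported as replicating an endpoint that includes fatal PE, and no planned analysis combines VTE with death to show whether the result holds once deaths are counted.

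**Working it through.** **1. The plan's own figure.** Section 10, pooled: 457.68226 expected events, assumed HR 1.12, margin 2, two-sided alpha 0.05. Power = Φ(√457.68/2 × ln(2/1.12) − 1.960) = Φ(10.697 × 0.5798 − 1.960) = Φ(4.242) = 0.99999. The stated 0.999988934 is reproduced.

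**2. Deaths against VTE in the run that used the study outcome.** Counts are from the censoring table in Section 7, patients and person-years from the Section 7 summary table. MarketScan is labelled Truven there.

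| | Deaths | VTE | Deaths/VTE | Patients | Person-years | Deaths per 1,000 PY | VTE per 1,000 PY |
|---|---|---|---|---|---|---|---|
| Optum | 118 | 232 | 0.51 | 17,355 | 6,152.63 | 19.2 | 37.7 |
| MarketScan | 63 | 482 | 0.13 | 32,388 | 12,258.57 | 5.1 | 39.3 |
| Medicare | 1,199 | 669 | 1.79 | 49,041 | 20,258.62 | 59.2 | 33.0 |
| Pooled | 1,380 | 1,383 | 1.00 | 98,784 | 38,669.82 | 35.7 | 35.8 |

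VTE ended follow-up in this run, so these deaths had no counted VTE before them. Medicare supplies 1,199/1,380 = 87% of them.

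**3. How much of the endpoint could be missing.** Let f be the share of these deaths that were fatal PE. The documents give no value, so f is an assumption. Missing share = f × deaths / (VTE + f × deaths).

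- f = 5%: 69/(1,383 + 69) = 4.8%
- f = 10%: 138/1,521 = 9.1%
- f = 20%: 276/1,659 = 16.6%
- f = 30%: 414/1,797 = 23.0%

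At f = 10% the share by database is 4.8% in Optum, 1.3% in MarketScan and 15.2% in Medicare. These figures concern recorded deaths only.

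**4. Deaths by arm.** Only Section 9 splits deaths by treatment: 259 of 15,893 on rivaroxaban and 218 of 15,893 on warfarin. Ratio 259/218 = 1.19. SE of the log = √(1/259 + 1/218) = 0.092, so the interval is about 0.99 to 1.42. That run used the dummy outcome, so VTE did not end follow-up, and the deaths may include some that followed an admission the real analysis would count.

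**5. Stress test against the margin.** Split the 457.68 expected events 1.12:1 (241.8 and 215.9), then add f × 259 and f × 218.

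- f = 10%: 267.7/237.7 = 1.126
- f = 30%: 319.5/281.3 = 1.136
- f = 100%: 500.8/433.9 = 1.154; with SE = 2/√934.7 the upper limit is about 1.31

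Power stays above 0.9999 throughout. This is a bounding exercise: it treats count ratios as hazard ratios, may count some fatal PE twice (step 4), and joins deaths from a table of 31,786 patients to events computed for 32,998.

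**The case against.** The strongest case on the other side is that the effect is small and the plan is not blind to it. Fatal PE admitted with PE coded first is captured. Table 3 will show deaths by arm. Even with every matched death counted, the event ratio moves only from 1.12 to 1.15 against a margin of 2.0. All of this stands, and it limits the point to endpoint match and possible informative censoring. Table 3 does not close the gap, because a count of censored deaths by arm is not an estimate of the treatment effect on VTE or death.

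A reader might infer three stronger things that the documents do not support:

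- *That half the endpoint is lost, because deaths equal VTE events.* The equality holds only for the pooled sum. By database the ratio runs from 0.13 to 1.79, and no cause of death is given.
- *That the censored deaths lean against rivaroxaban.* The interval for 1.19 includes 1, and the deaths come from the dummy-outcome run. Shorter median follow-up on rivaroxaban does not rescue the inference. In MarketScan the medians are 91 and 92 days, and the upper quartiles are longer on rivaroxaban in Optum (175 against 173) and MarketScan (188 against 178).
- *That 0.7%, 0.2% and 2.4% are death-capture rates.* They are the proportions whose follow-up ended in a recorded death. Mean ages by arm are about 60–62 in Optum, 54–56 in MarketScan and 74–75 in Medicare, so age, incomplete capture or both could explain the differences.

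**Conclusion.** The mismatch is real and follows from the definitions alone: the endpoint to be replicated includes fatal PE, the coded outcome captures it only through an inpatient primary diagnosis, and death censors in both AT and ITT.

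The size is bounded, not known. Under the assumed 5–30% share, between 4.8% and 23.0% of the pooled composite would be uncounted, with the loss concentrated in Medicare. The direction of any bias in the hazard ratio cannot be derived from the documents. Nothing computed here brings the result near 2.0 or weakens power, so this is no ground for doubting the non-inferiority test on hospitalised VTE. It is a ground for not extending that conclusion to fatal PE without a supporting analysis. This is an inexpensive improvement, best settled before the comparative analyses, for which Section 13 shows no date.

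**What to change.** 1. Keep the coded outcome as primary, but call it *hospitalised VTE (inpatient primary diagnosis)* in Section 6.3.1 and in the conclusions. Leave Section 1.3 alone, since it describes the trial's outcome.
2. In Sections 6.3.1 and 13.2, pre-specify one supportive analysis, AT and ITT, with the event defined as VTE hospitalisation or death from any cause. Report it by database and read it against the trial composite in Appendix A (HR 0.85, 0.63 to 1.14).
3. Give most weight to Medicare, where 1,199 of the 1,380 deaths are recorded. State that the low MarketScan figure may reflect age, incomplete capture or both.
4. Use the result to qualify what is said about fatal PE. It should not be a pass/fail condition unless a criterion is set in advance.

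The cost is wording plus AT and ITT fits in three databases (2 × 3 = 6) on data sources already in use. The drawback is dilution: many of the added deaths may not be due to PE, and in Medicare deaths would outnumber VTE events in the composite, so it can support the primary analysis but not replace it.
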